s. Subjects will be monitored for disease worsening (vIGA-ADTM ≥2), and study drug may be started at any time during the observation period. If an unscheduled visit is required for re-start of study drug, then the vIGA-ADTM must be completed.

t. For subjects receiving study drug, subjects or their caregivers will be instructed to apply study drug QD at the approximate same time each day, based on subject or caregiver preference.

u. For subjects receiving study drug, study drug will be applied after safety assessments have been conducted, [REDACTED]

v. Subjects who withdraw from the study before Visit 13 (Week 48) will complete an ET visit. A follow-up visit is not required for a subject who early terminates.

w. Phone calls to assess AEs and concomitant medications, to review study drug application procedures (if applicable), and to confirm subject's continued participation in the study. Subjects should be reminded to complete the diary and bring it with them to the next clinic visit.

AD = atopic dermatitis; AE = adverse event (s); BMI = body mass index; %BSA = percent body surface area; C = collect; [REDACTED]; CRF = case report form; CV = cardiovascular; D = dispense; [REDACTED]; ET = early termination; EASI = Eczema Area and Severity Index; FU = follow-up; [REDACTED]; NA = not applicable; P/C = phone call; PK = pharmacokinetic;

[REDACTED]; PP-NRS = Peak Pruritus-Numeric Rating Scale; QD = once daily; WOCBP = women of child-bearing potential; V = visit; vIGA-ADTM = Validated Investigator Global Assessment in Atopic Dermatitis.

1 Introduction

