3.1 Overall Design

This is an open-label, long-term multicenter, study to evaluate the safety and efficacy of topical tapinarof cream, 1% in subjects with AD. Subjects in this study will have either: a) completed treatment with tapinarof or vehicle in one of two Phase 3 pivotal safety and efficacy studies, DMVT-505-3101 or DMVT-505-3102, and rolled over into this study; b) completed treatment with tapinarof in the Phase 2 maximal use PK study, DMVT-505-2104, and rolled over into this study; or c) enrolled directly into this study. This study will consist of up to 48 weeks of treatment and a 1-week safety follow-up period.

At the completion of the Week 8 visit of study DMVT-505-3101 or study DMVT-505-3102 or the Day 28 visit of study DMVT-505-2104 (Baseline [Day 1] in this study), all eligible subjects will be offered enrollment in this OL-LTE study. Approximately 125 additional pediatric subjects ages 2 to < 18 years who are not eligible for participation in the Phase 3 pivotal studies (DMVT-505-3101 or DMVT-505-3102) will be enrolled directly into this OL-LTE study. Study visits during the treatment period for all subjects will occur every 4 weeks (\pm 3 days). Unscheduled visits may occur, as needed. Subjects who withdraw from the study before Week 48 will return to the study site for an Early Termination visit. The total duration of subject participation in this study will be approximately 49 weeks for rollover subjects (Baseline to Follow-Up) and approximately 53 weeks for direct-enrolling subjects (Screening to Follow-Up).

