4.5.2 Withdrawal Procedures

The primary reason for the discontinuation of study drug and/or withdrawal from study must be recorded in the source document and on the case report form (CRF). If a subject is prematurely discontinued from study drug, the Investigator must make every effort to perform an Early Termination Visit (Section 7.7) and document the primary reason for withdrawal.

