7.5 Follow-Up Visit 14; Week 49 (Day 344 ±3 Days)

Subjects will return to the study site 1 week (± 3 days) after last treatment to complete follow-up assessments as follows:

- Brief physical examination
- Vital signs measurement
- Blood sample collection for clinical laboratory tests (serum chemistry and hematology)
- Urinalysis
- vIGA-AD™ score (excluding subject's scalp)
- %BSA affected calculation (excluding subject's scalp)
- EASI (excluding subject's scalp)
- [REDACTED]
- [REDACTED]
- PP-NRS (by subject or caregiver)
- [REDACTED]
- [REDACTED]

- AE recording
- Concomitant medication recording

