7.7 Early Termination Visit

Subjects who withdraw early from the study will be asked to return to the study site to complete early termination assessments as follows:

- Brief physical examination
- Vital signs measurement
- Urine pregnancy test (WOCBP)
- Blood sample collection for clinical laboratory tests (serum chemistry and hematology)
- Urinalysis
- vIGA-AD™ score (excluding subject's scalp)
- %BSA affected calculation (excluding subject's scalp)
- EASI (excluding subject's scalp)

- [REDACTED]
- [REDACTED]
- [REDACTED]
- PP-NRS (by subject or caregiver)
- [REDACTED]
- [REDACTED]
- [REDACTED]
- [REDACTED]
- [REDACTED]
- AE recording
- Concomitant medication recording
- Collect subject diaries
- Review subject diaries for treatment compliance
- Collect study drug

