8.1 Adverse Events, Serious Adverse Events, and Adverse Events of Special Interest

The Investigator or site staff is responsible for detecting, documenting, and reporting events that meet the definition of an AE, SAE, or adverse event of special interest (AESI). At each visit/contact, subjects should be questioned in a general way so as not to introduce bias in detecting AEs and/or SAEs. Open-ended and non-leading verbal questioning of the subject is the preferred method to inquire about AE occurrence.

Investigators are not obligated to actively seek AEs or SAEs in former study subjects. However, if the Investigator learns of any SAE, including a death, at any time after a subject has been discharged from the study, and he/she considers the event reasonably related to the study drug or study participation, the Investigator should promptly notify the Sponsor.

A narrative will be written and included in the Clinical Study Report for all SAEs and AESIs, and for all AEs that lead to study discontinuation

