8.3 Time Period and Frequency for Event Assessment and Follow-Up

8.3.1 Adverse Event Reporting

All AEs will be collected from the time of signed informed consent until the final visit.

Any AEs assessed as related to study participation (e.g., protocol mandated procedures, invasive tests, or change in existing therapy) will be collected from the time a subject consented to participate in the study up to and including any follow-up contact.

All SAEs will be recorded on the CRF and reported to the Sponsor within 24 hours via email or phone (refer to [Medical Monitor / Sponsor Information Page](#) for contact information) (see Section 8.4).

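### Subjects who withdraw before Week 48 have no scheduled adverse event contact after an Early Termination visit that is not timed to the last dose, so new events just after stopping can go uncollected

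*Protocol*

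**What the plan says.** Protocol Section 3.1 describes the design: "This study will consist of up to 48 weeks of treatment and a 1-week safety follow-up period". Section 7.5 brings subjects back one week, plus or minus 3 days, "after last treatment to complete follow-up assessments as follows"; AE recording is on its list.

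Table 1 footnote v makes an exception for those who leave early: "Subjects who withdraw from the study before Visit 13 (Week 48) will complete an ET visit". It then adds: "A follow-up visit is not required for a subject who early terminates".

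Two sections describe the ET visit, and neither times it to the last dose. Section 7.7 says "Subjects who withdraw early from the study will be asked to return to the study site to complete early termination assessments as follows", with AE recording on the list. Section 4.5.2 says "If a subject is prematurely discontinued from study drug, the Investigator must make every effort to perform an Early Termination Visit".

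On when collection ends, Section 8.3.1 says "All AEs will be collected from the time of signed informed consent until the final visit". Section 6.2.1 puts the end at the last visit or contact, which is not quite the same. For former subjects, Section 8.1 says "Investigators are not obligated to actively seek AEs or SAEs in former study subjects". It does require prompt notification of an SAE that the investigator learns of after discharge and considers reasonably related.

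**The concern.** Safety and tolerability is the first objective. A completer still on drug at Week 48 has a planned AE assessment about a week after stopping. A subject who withdraws may be seen on or just after the last dosing day and then not asked again. A new AE starting in the following days would reach the database only by chance.

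This is a gap in collection, not in analysis. The treatment-emergent definition in SAP Section 13.2 has no cut-off after the last dose, so such an event would be counted if it were recorded. The same section tabulates events with onset after 48 weeks, so events in the completers' follow-up week can be reported. AE percentages can use all subjects as the denominator (SAP Section 6), so uncollected events would lower the reported incidence slightly.

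**Working it through.** The plan gives no figure of its own here. The check has two parts: a reading of the sections against each other, and an illustrative size.

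**Observation after the last dose**

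- Completer dosed to Week 48: Day 344 − Day 337 = 7 days, which agrees with the one-week follow-up. The ±3 days in Section 7.5 gives 7 − 3 = 4 to 7 + 3 = 10 days.
- Early terminator: the required time after the ET visit is 0 days. Time off drug with AE ascertainment equals the gap between last dose and ET visit. That gap is unspecified, so it may be near 0 or longer than a week.

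**Do other provisions fill the gap?**

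| Protocol section | What it covers | New AEs after the ET visit? |
|---|---|---|
| 8.3.2 | AEs already reported, until resolved, stable, explained or lost to follow-up | Not solicited |
| 8.2.1.2.2, 8.2.1.2.3 | Weekly follow-up when a Grade 3 or 4 AE requires permanent discontinuation, until that AE resolves or is stable | Contact exists, but for the known AE |
| 8.2.1.2.1 | Withdrawal for a Grade 1 or 2 AE | Termination evaluations only |
| 8.2.2 | Related AEs, through any follow-up contact | Only if a contact takes place |
| 8.1 | Related SAEs learned of after discharge | Passive only |

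None of these schedules a contact to ask about new AEs in subjects who leave for non-AE reasons or for a Grade 1 or 2 AE.

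**Illustrative number of events**

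The documents give no dropout rate or AE rate. Assume 15% to 30% of the maximum 961 subjects terminate early, 1 to 3 AEs per subject-year, and a full week lost by each.

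- Subjects: 961 × 0.15 ≈ 144; 961 × 0.30 ≈ 288.
- Events, low: 144 × 7/365.25 × 1 ≈ 2.8.
- Events, high: 288 × 7/365.25 × 3 ≈ 16.6.

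**Illustrative share of person-time**

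Take a wider dropout range of 10% to 40%, with withdrawal on average halfway (24 weeks) and 49 weeks for completers.

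- 10%: 96 / (865 × 49 + 96 × 24) = 96 / 44,689 ≈ 0.2%.
- 40%: 384 / (577 × 49 + 384 × 24) = 384 / 37,489 ≈ 1.0%.

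**The case against.** The best defence is that the ET visit is itself a safety contact. It includes AE recording, physical examination, vital signs, laboratory tests and urinalysis, and Section 4.5.2 links it to drug having been stopped. Under the intermittent regimen in Section 5.1.5.1, a subject who withdraws while clear and off treatment may already be more than a week past the last dose. This stands. It rules out the tempting reading that early terminators have no post-treatment AE contact at all.

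A reader might also infer that everyone who stopped drug for an AE goes unobserved. The documents do not support that. Grade 3 and 4 discontinuations are followed weekly, and reported AEs are followed to an outcome. Section 8.1.3 allows drug to be stopped for an AE of special interest and restarted, with no requirement to leave the study. The AE-related part of the gap is mainly withdrawal from the study for a Grade 1 or 2 event.

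Two further inferences should be set aside. No passage reports contact dermatitis or follicular events first appearing after drug is stopped, so a claim that delayed local reactions are being missed would be speculation. Comparability of AE counts between completers and early terminators matters little: no such comparison is planned, summaries are by route of entry without testing, and observation time already differs between these groups by up to 48 weeks.

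Finally, the waiver is a deliberate design choice with a small effect. That is fair, and it limits the weight of the point. It does not explain why the stated follow-up week should lapse when a phone call could preserve it.

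**Conclusion.** The point holds as a gap for new AEs, not as a general absence of safety follow-up. Early terminators have no scheduled AE contact after the ET visit, and their off-drug observation is whatever the untimed interval before that visit happens to be. The subjects mainly affected are those leaving for non-AE reasons or for Grade 1-2 AEs.

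The size is modest: about 3 to 17 AEs under the assumed dropout and AE rates, or roughly 0.2% to 1% of person-time under the wider dropout range. Both figures lean high because they charge a full lost week to every early terminator, and some will have an ET visit days after the last dose. A higher AE rate among those who leave would raise the event count. This is an inexpensive improvement to the completeness of the safety data and does not threaten the study's conclusions.

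**What to change.** In Table 1 footnote v and Section 7.7, add one phone contact 7 (±3) days after the last dose for early terminators who agree to it. Record AEs and concomitant medications, as the Week 2 call in Section 7.4 already does. Skip the call when the ET visit is at least 7 days after the last dose.

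Reconcile Sections 6.2.1 and 8.3.1 so that both say collection of all AEs, related or not, runs to that contact, or to the ET visit when the call is skipped.

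The cost is a small amendment and one call per early terminator, with no extra visit, sample or staff. Some subjects will not be reachable, so the gap will narrow but not close.

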1.1 Background Information and Study Rationale

1.1.1 Background Information

Atopic dermatitis (AD) (also called atopic eczema) is an intensely pruritic, chronic, relapsing, inflammatory skin disease [Bieber, 2008]. The characteristic signs and symptoms of AD include sensations of pruritis and burning, xerosis, erythematous papules and plaques, exudation, crusting, and lichenification. Quality of life is affected through sleep deprivation due to the intense and constant itching, as well as the stigma associated with having a visible skin disease [Carroll, 2005; Lewis-Jones, 2006]. Up to 30% of children may be affected by AD at some point, and 2% to 10% of adults have AD [Bieber, 2008]. Currently there is no curative therapy. Stabilizing the disease and reducing the number and severity of flares are the primary goals of treatment. Topical treatments directed at skin inflammation are a key factor in disease management, as is symptomatic relief of itching. Although multiple topical treatment options are available, there still remains a need for a topical treatment that combines a high level of efficacy with an acceptable safety profile that permits application to a large body surface area (BSA) without restrictions on duration of treatment.

Tapinarof (DMVT-505), formerly known as GSK2894512 and WBI-1001, is a fully synthetic naturally identified stilbene that is being developed by Dermavant Sciences, Inc. (Dermavant) as a novel anti-inflammatory agent for the topical treatment of AD and plaque psoriasis. The compound (number WBI-1001) was initially developed by Welichem Biotech Inc. (Welichem; Burnaby, British Columbia, Canada) and then was acquired by GlaxoSmithKline (GSK) on 31 July 2012 for further development in the rest of the world except China. Dermavant acquired the drug from GSK on 20 August 2018 for continued development in all other territories. Development of tapinarof cream in Japan is being jointly pursued with Japan Tobacco Inc. (JT), with a Phase 3 program in PSO and AD scheduled to commence in late 2021. In China, the compound was independently developed by Beijing Wenfeng Tianji Pharmaceutical Technology Co. (BWTP) (Shenzhen Celestial) under the name benvitimod (active ingredient corresponds to tapinarof). BWTP was granted authorization to market benvitimod cream (a different formulation and excipient profile compared to tapinarof cream) as Symbiox® in China in July 2019.

Tapinarof cream, 1% is a white to off-white, oil-in-water emulsion intended for topical application to AD and psoriatic skin lesions, which has a novel mechanism of action. Tapinarof is a nonsteroidal, small molecule therapeutic aryl hydrocarbon receptor (AhR) modulating agent (TAMA), which exerts its therapeutic effects via agonism of AhR, a cytosolic ligand-dependent transcription factor. Upon ligand binding, AhR translocates to the nucleus and dimerizes with AhR nuclear translocator (ARNT) forming an AhR-ARNT heterodimer [Smith, 2017]. The AhR-ARNT heterodimer modulates gene transcription through direct and indirect interaction with DNA. By activation of this AhR signaling pathway, tapinarof has the potential to downregulate the expression of pro-inflammatory cytokines, including interleukin (IL)-4, IL-5, IL-6, IL-13, IL-17A and F, and eotaxin, and upregulate the expression of several skin barrier proteins, including filaggrin, hornerin, and involucrin. In addition, AhR also activates the antioxidative transcription factor nuclear factor-erythroid 2-related factor-2 (Nrf2), upregulating the expression of antioxidative enzymes [Smith, 2017; Furue, 2019]. By targeting AhR, tapinarof has a biological profile that differs from that of currently available products, offering patients a truly novel therapeutic treatment option for plaque psoriasis and AD.

Two Phase 2b, 12-week, randomized, double-blind, vehicle-controlled, 6-arm, parallel group, dose-finding studies with topically applied tapinarof cream were conducted by GSK; 1 study each in subjects with AD or psoriasis. These 2 studies evaluated the safety and efficacy of tapinarof cream (Formulation F) at

2 concentrations (0.5% or 1% weight/weight [w/w]) and 2 application frequencies (once daily [QD] or twice daily [BID]) in 247 adult and adolescent subjects with AD and in 227 adult subjects with plaque psoriasis. In both studies, tapinarof showed a clear therapeutic effect compared with vehicle, with the 1% w/w concentration treatment groups demonstrating a higher proportion of subjects with treatment success compared with the 0.5% w/w concentration groups (applied QD and BID in the AD study). In both indications, the tapinarof 1% dosing groups showed a faster onset of action than the 0.5% dosing groups, and QD application had similar efficacy to BID application. In both Phase 2b studies, tapinarof showed an acceptable safety profile. Treatment-emergent adverse events (TEAEs) were reported with a higher frequency in the tapinarof groups than in the vehicle groups. The most frequent TEAEs ($\geq 5\%$ in any arm or in total) were nasopharyngitis, folliculitis, dermatitis contact, atopic dermatitis, upper respiratory tract infection, headache, vomiting, acne, application site dermatitis, miliaria, dermatitis allergic, and impetigo. The majority of TEAEs were mild or moderate in severity. In each study, the tapinarof 1% QD treatment group had a lower frequency of TEAEs than the tapinarof 1% BID treatment group.

Tapinarof has been evaluated in two identical Phase 3, 12-week, randomized, double-blind, vehicle-controlled trials in adult subjects with plaque psoriasis. These studies evaluated the safety and efficacy of tapinarof cream, 1% QD versus vehicle cream QD in a combined 1025 subjects randomized 2:1 tapinarof to vehicle. In both trials, tapinarof demonstrated superiority against vehicle on the primary endpoint, a Physician Global Assessment (PGA) score of 0 (clear) or 1 (almost clear) with a 2-point improvement at Week 12. In addition, tapinarof was highly statistically significant compared to vehicle on all secondary endpoints which included proportion of subjects achieving a 75% improvement in the Psoriasis Area and Severity Index, a PGA score of 0 or 1, change in percent body surface area (%BSA), and proportion of subjects achieving a 90% improvement in the Psoriasis Area and Severity Index at Week 12. TEAEs were reported with a higher frequency in the tapinarof group than in the vehicle group. The most frequent TEAEs ($\geq 5\%$ in any arm or in total) were folliculitis, nasopharyngitis, and contact dermatitis. The majority of TEAEs were mild or moderate in intensity.

Tapinarof has also been evaluated in an open-label, long-term extension (OL-LTE) study in adult subjects with plaque psoriasis. The OL-LTE study in adults with plaque psoriasis evaluated the safety and efficacy of tapinarof cream, 1% QD for 40 weeks in 763 subjects enrolled from the two identical 12-week studies. While the study remains ongoing at this time, in a pre-specified interim analysis of the study tapinarof demonstrated continued and substantial improvement in efficacy endpoints beyond the 12 weeks of treatment observed in the identical Phase 3 studies. A high rate of complete disease clearance was achieved, with a remittive effect of approximately 4 months of disease control off therapy. Tapinarof was well tolerated with long-term use and had a safety profile consistent with previous studies.

1.1.2 Study Rationale

This 48-week, Phase 3, OL-LTE study is being conducted as part of a clinical development program to evaluate the long-term safety and continued efficacy of tapinarof cream, 1% for the treatment of AD in children and adults. Subjects who complete one of three parent studies (Phase 3 pivotal safety and efficacy study DMVT-505-3101, Phase 3 pivotal safety and efficacy study DMVT-505-3102, or Phase 2 maximal use pharmacokinetics [PK] study DMVT-505-2104) and meet the predefined criteria will have the option to participate in this study. Additionally, approximately 125 pediatric subjects ages 2 to < 18 years who are not eligible for participation in the Phase 3 pivotal studies will also be enrolled directly into this OL-LTE study.

1.3.2 Benefit Assessment

Subjects may experience improvements in their AD during the course of the study and may benefit from the additional safety assessments conducted as part of the study (e.g., physical examination, laboratory tests). Subjects in the study will also contribute to the process of developing a novel anti-inflammatory agent for the topical treatment of AD.

3.1 Overall Design

This is an open-label, long-term multicenter, study to evaluate the safety and efficacy of topical tapinarof cream, 1% in subjects with AD. Subjects in this study will have either: a) completed treatment with tapinarof or vehicle in one of two Phase 3 pivotal safety and efficacy studies, DMVT-505-3101 or DMVT-505-3102, and rolled over into this study; b) completed treatment with tapinarof in the Phase 2 maximal use PK study, DMVT-505-2104, and rolled over into this study; or c) enrolled directly into this study. This study will consist of up to 48 weeks of treatment and a 1-week safety follow-up period.

At the completion of the Week 8 visit of study DMVT-505-3101 or study DMVT-505-3102 or the Day 28 visit of study DMVT-505-2104 (Baseline [Day 1] in this study), all eligible subjects will be offered enrollment in this OL-LTE study. Approximately 125 additional pediatric subjects ages 2 to < 18 years who are not eligible for participation in the Phase 3 pivotal studies (DMVT-505-3101 or DMVT-505-3102) will be enrolled directly into this OL-LTE study. Study visits during the treatment period for all subjects will occur every 4 weeks (\pm 3 days). Unscheduled visits may occur, as needed. Subjects who withdraw from the study before Week 48 will return to the study site for an Early Termination visit. The total duration of subject participation in this study will be approximately 49 weeks for rollover subjects (Baseline to Follow-Up) and approximately 53 weeks for direct-enrolling subjects (Screening to Follow-Up).

Rollover subjects in this study will begin treatment based on their vIGA-ADTM score from the final visit in one of the three aforementioned studies (DMVT-505-3101, DMVT-505-3102, or DMVT-505-2104). Subjects entering with a vIGA-ADTM \geq 1 will receive treatment with tapinarof cream, 1% QD until they achieve a vIGA-ADTM score of 0, at which time treatment will be discontinued and subjects monitored for maintenance of disease control (i.e., the extent of the remittive effect). If/when disease worsening occurs, as evidenced by a flare to vIGA-ADTM \geq 2, treatment will then be re-initiated and continued until a vIGA-ADTM of 0 is achieved. Subjects entering with a vIGA-ADTM of 0 will have treatment discontinued beginning at the Baseline visit and will be monitored for maintenance of the remittive effect. If/when disease worsening occurs, as evidenced by a vIGA-ADTM \geq 2, treatment will then be re-initiated and continued until a vIGA-ADTM of 0 is achieved. This treatment and re-treatment pattern of use will be continued until the end of the study (i.e., subjects may receive study treatment up until the Week 48 visit) (see Section 5.1.5.2 for additional details).

Subjects enrolling directly into this study will receive treatment QD with tapinarof cream, 1% beginning at Baseline and continue treatment until they achieve a vIGA-ADTM score of 0, at which time treatment will be discontinued and subjects monitored for maintenance of the remittive effect. If/when disease worsening occurs, as evidenced by a flare to vIGA-ADTM \geq 2, treatment will be re-initiated and continued until a vIGA-ADTM of 0 is achieved. This regimen of treatment and re-treatment will continue until the end of the study (i.e., subjects may receive study drug up until the Week 48 visit) (see Section 5.1.5.2 for additional details).

Study drug will be dispensed to subjects or their caregivers, applied during the clinic visits, and applied at home between clinic visits as instructed by site personnel. Subjects or their caregivers will be instructed to apply study drug QD to all affected areas, including newly appearing lesions and lesions/areas that improve during the study until a vIGA-ADTM of 0 is achieved. Once a vIGA-ADTM of 0 is achieved, the treatment period ends. If/when disease worsening occurs, and treatment is re-initiated at a vIGA-ADTM of \geq 2, all lesions currently present and any new lesions that occur during the new treatment period should be treated.

Subjects or their caregivers will apply sufficient study drug to cover each lesion completely with a thin layer of study drug and will record the time of study drug application and daily itch score (PP-NRS) in a daily diary provided by the study site. Subjects are allowed, but not required, to treat scalp lesions with study drug; however, efficacy analyses will not include assessment of AD on the scalp. At the first clinic visit, if applicable, subjects and/or caregivers will be instructed to maintain the approximate dosing time for the daily application of study drug. At the phone contact at Week 2, subjects or caregivers should be reminded to complete their daily diary and bring it with them to the next clinic visit.

Study drug application instructions will be reviewed at all post-randomization clinic visits and during any planned study phone calls. On clinic visit days, subjects and/or caregivers will be instructed/reminded on how to apply study drug (except during the final treatment/end-of-study visits). During the clinic visits, subjects or their caregivers will apply the daily dose of study drug while on-site under the supervision of site personnel, after efficacy and safety assessments have been completed [REDACTED]. The time of the dose application and assessments will depend on the time of the clinic visit. Therefore, the timing of the clinic visit may lead to a change in the subject's chosen dosing time for that day.

Safety assessments will include AEs, clinical laboratory tests, physical examination, vital signs, and LTS. Efficacy assessments will include vIGA-AD™ score, %BSA affected, EASI, PP-NRS, [REDACTED]

Refer to Section 6 for descriptions of study procedures and assessments and Section 7 and Table 1 for timing of procedures and assessments.

